11.9 Investigator Obligations

The Principal Investigator is responsible for the conduct of the clinical trial at the site in accordance with Title 21 of the Code of Federal Regulations and/or the Declaration of Helsinki. The PI is responsible for personally overseeing the treatment of all study patients. The PI must assure that all study site personnel, including sub-investigators and other study staff members, adhere to the study protocol and all FDA/GCP/NCI regulations and guidelines regarding clinical trials both during and after study completion.

The Principal Investigator at each institution or site will be responsible for assuring that all the required data will be collected, entered onto the appropriate eCRFs, and submitted within the study-specific timeframes. Periodically, monitoring visits may be conducted and the Principal Investigator will provide access to his/her original records to permit verification of proper entry of data. The study may also be subject to routine audits by the Audit Committee, as outlined in the DSMP.

11.10 Publication Policy

Neither the complete nor any part of the results of the study carried out under this protocol, nor any of the information provided by the sponsor ([name]) for the purposes of performing the study, will be published or passed on to any third party without the consent of [name]. Results of this study may be used for teaching, research, publications, or presentations at scientific meetings.

All potential publications and/or data for potential publications (e.g. manuscripts, articles, data, text, diagrams, abstracts, posters, charts, slides, pictures, or clinicaltrials.gov releases) must be approved in accordance with the policies and processes set forth in the Lurie Cancer Center DSMP. For trials that require high intensity monitoring, the assigned QAM will prepare a preliminary data summary (to be approved by the DSMC) no later than 3 months after the study reaches its primary completion date (the date that the final subject is examined or receives an intervention for the purposes of final data collection for the primary endpoint). If the investigator's wish to obtain DSMC-approved data prior to this point (or prior to the point dictated by study design), the PI must send a written request for data to the QAM which includes justification. If the request is approved, data will be provided no later than 4 weeks after this request approval. The data will be presented to the DSMC at their next available meeting, and a final, DSMC-approved dataset will be released along with any DSMC decisions regarding publication. The investigators are expected to use only DSMC-approved data in future publications.

NU Study Number: *NU 16101*
BMS Study Number: *CA 209-615*

The investigators should submit a copy of the manuscript to the biostatistician to confirm that the DSMC-approved data are used appropriately. Once the biostatistician gives final approval, the manuscript may be submitted to external publishers.

NU shall provide BMS with a copy of each Publication at the earliest practicable time, but in any event not less than thirty (30) days prior to its submission to a journal, publisher or meeting or fifteen (15) days prior to any public disclosure of any manuscript or other public disclosure (e.g., presentations). To the extent applicable, BMS personnel shall be acknowledged (including authorship where applicable) in accordance with customary scientific practice.

REFERENCES

APPENDIX 1:

Treatment-Emergent Serious Adverse Events from 5 Clinical Studies (N=121) for Patients Undergoing TheraSphere® Treatment Therapy

Expected Adverse Device Effects	
Adverse Device Effect	Expected Frequency (%)
TheraSphere	
Elevated alkaline phosphatase	75
Elevated SGOT	75
Elevated SGPT	75
Lymphocyte depression (asymptomatic)	35
Fatigue	29
Fever	25
Nausea	15
Heartburn	14
Vomiting	15
Pain	15
Decreased albumin	10
Ascites	10
Elevated bilirubin	10
Pleural effusion	10
Ulcer, GI	10
Anorexia	10
Constipation	5
Dizziness	5
Muscle pain	5
Renal Failure	5
Cholecystitis	< 5
Pneumonitis	< 1
Death	< 1
Angiographic Procedure	
Allergic reaction (e.g. contrast media)	< 5
Medication reaction (e.g. nausea from narcotics)	< 5
Vascular spasm	< 1
Vessel dissection	< 1
Vessel rupture	< 1
Thrombosis / embolism (vascular access)	< 1
Bleeding / Hematoma	< 1
Infection	< 1
Venipuncture	
Discomfort/pain	5
Fainting	< 1
Bleeding at site	< 1
Infection	< 1

APPENDIX 2:

Pregnancy and Contraception Requirements

Investigators shall counsel WOCBP and male subjects who are sexually active with WOCBP on the importance of pregnancy prevention and the implications of an unexpected pregnancy. Investigators shall advise WOCBP and male subjects who are sexually active with WOCBP on the use of highly effective methods of contraception from the time of treatment initiation to 5 months (for FOCBP) or 7 months (for males with FOCBP partners) after the last dose of nivolumab. Highly effective methods of contraception have a failure rate of < 1% per year when used consistently and correctly.

At a minimum, subjects must agree to the use of two methods of contraception, with one method being highly effective and the other method being either highly effective or less effective as listed below:

HIGHLY EFFECTIVE METHODS OF CONTRACEPTION

Male condoms with spermicide

- a) Hormonal methods of contraception including combined oral contraceptive pills, vaginal ring, injectables, implants, and intrauterine devices (IUDs) such as Mirena® by WOCBP subject or male subject's WOCBP partner. Female partners of male subjects participating in the study may use hormone based contraceptives as one of the acceptable methods of contraception since they will not be receiving study drug.
- b) Nonhormonal IUDs, such as ParaGard®
- c) Tubal ligation
- d) Vasectomy.
- e) Complete Abstinence*

*Complete abstinence is defined as complete avoidance of heterosexual intercourse and is an acceptable form of contraception for all study drugs. Subjects who choose complete abstinence are not required to use a second method of contraception, but female subjects must continue to have pregnancy tests. Acceptable alternate methods of highly effective contraception must be discussed in the event that the subject chooses to forego complete abstinence.

LESS EFFECTIVE METHODS OF CONTRACEPTION

- a) Diaphragm with spermicide
- b) Cervical cap with spermicide
- c) Vaginal sponge
- d) Male Condom without spermicide*
- e) Progestin only pills by WOCBP subject or male subject's WOCBP partner
- f) Female Condom*

*A male and female condom must not be used together

[figure not shown]
Azoospermic males and WOCBP who are continuously not heterosexually active are exempt from contraceptive requirements. However they must still undergo pregnancy testing as described in this section.

APPENDIX 3:

Recommended management algorithms for suspected nivolumab related endocrinopathy, gastrointestinal toxicity, hepatotoxicity, neurologic toxicity, pulmonary toxicity, renal toxicity and skin toxicity

Endocrinopathy Management Algorithm

[figure not shown]
Rule out non-inflammatory causes. If non-inflammatory cause, treat accordingly and continue I-O therapy. Consider visual field testing, endocrinology consultation, and imaging.

Patients on IV steroids may be switched to an equivalent dose of oral corticosteroids (e.g. prednisone) at start of tapering or earlier, once sustained clinical improvement is observed. Lower bioavailability of oral corticosteroids should be taken into account when switching to the equivalent dose of oral corticosteroids.

GI Adverse Event Management Algorithm

[figure not shown]
Rule out non-inflammatory causes. If non-inflammatory cause is identified, treat accordingly and continue I-O therapy. Opiates/narcotics may mask symptoms of perforation. Infliximab should not be used in cases of perforation or sepsis.

Patients on IV steroids may be switched to an equivalent dose of oral corticosteroids (e.g. prednisone) at start of tapering or earlier, once sustained clinical improvement is observed. Lower bioavailability of oral corticosteroids should be taken into account when switching to the equivalent dose of oral corticosteroids.

Hepatic Adverse Event Management Algorithm

Rule out non-inflammatory causes. If non-inflammatory cause, treat accordingly and continue I-O therapy. Consider imaging for obstruction.

[figure not shown]
Patients on IV steroids may be switched to an equivalent dose of oral corticosteroids (e.g. prednisone) at start of tapering or earlier, once sustained clinical improvement is observed. Lower bioavailability of oral corticosteroids should be taken into account when switching to the equivalent dose of oral corticosteroids.

*I-O therapy may be delayed rather than discontinued if AST/ALT ≤ 8 x ULN or T.bili ≤ 5 x ULN.

**The recommended starting dose for grade 4 hepatitis is 2 mg/kg/day methylprednisolone IV.

Neurological Adverse Event Management Algorithm

[figure not shown]
Rule out non-inflammatory causes. If non-inflammatory cause, treat accordingly and continue I-O therapy.

Patients on IV steroids may be switched to an equivalent dose of oral corticosteroids (e.g. prednisone) at start of tapering or earlier, once sustained clinical improvement is observed. Lower bioavailability of oral corticosteroids should be taken into account when switching to the equivalent dose of oral corticosteroids.

Pulmonary Adverse Event Management Algorithm

[figure not shown]
Rule out non-inflammatory causes. If non-inflammatory cause, treat accordingly and continue I-O therapy. Evaluate with imaging and pulmonary consultation.

Patients on IV steroids may be switched to an equivalent dose of oral corticosteroids (e.g. prednisone) at start of tapering or earlier, once sustained clinical improvement is observed. Lower bioavailability of oral corticosteroids should be taken into account when switching to the equivalent dose of oral corticosteroids.

Renal Adverse Event Management Algorithm

[figure not shown]
Rule out non-inflammatory causes. If non-inflammatory cause, treat accordingly and continue I-O therapy

Patients on IV steroids may be switched to an equivalent dose of oral corticosteroids (e.g. prednisone) at start of tapering or earlier, once sustained clinical improvement is observed. Lower bioavailability of oral corticosteroids should be taken into account when switching to the equivalent dose of oral corticosteroids.

Skin Adverse Event Management Algorithm

Rule out non-inflammatory causes. If non-inflammatory cause, treat accordingly and continue I-O therapy.

Patients on IV steroids may be switched to an equivalent dose of oral corticosteroids (e.g. prednisone) at start of tapering or earlier, once sustained clinical improvement is observed. Lower bioavailability of oral corticosteroids should be taken into account when switching to the equivalent dose of oral corticosteroids.

*Refer to NCI CTCAE v4 for term-specific grading criteria.

**If SJS/TEN is suspected, withhold I-O therapy and refer patient for specialized care for assessment and treatment. If SJS or TEN is diagnosed, permanently discontinue I-O therapy.

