4.4 Toxicity Management: Dose Delays and Discontinuation

Dosing with Yttrium-90 will follow standard of care procedures, and there will be no dose modifications.

Any patient who receives at least one dose of nivolumab will be evaluable for toxicity endpoints. Each patient will be assessed for the development of toxicity by laboratory results and physical exam at each study visit, according to CTCAE 4.03.

Nivolumab may be delayed or discontinued following the instructions detailed in section 4.4.1.

In addition, nivolumab should be discontinued for toxicities as outlined in section 4.4.2.

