4.4.1 Dosing delays

There will be no dose modifications allowed for management of toxicities.

Patients will be allowed to delay nivolumab treatment by up to 6 weeks.

Nivolumab administration should be delayed for the following until resolution to \leq Grade 1 or baseline:

- Any Grade ≥ 2 non-skin, drug-related adverse event, with the following exceptions:
 - Grade 2 drug-related fatigue or laboratory abnormalities do not require a treatment delay
- Any Grade 3 skin, drug-related adverse event
- Any Grade 3 drug-related laboratory abnormality, with the following exceptions for lymphopenia, leukopenia, AST, ALT, or total bilirubin:
 - Grade 3 lymphopenia or leukopenia does not require dose delay
 - If a subject has a baseline AST, ALT or total bilirubin that is within normal limits, delay dosing for drug-related Grade ≥ 2 toxicity
 - If a subject has baseline AST, ALT, or total bilirubin within the Grade 1 or 2 toxicity range, delay dosing for drug-related Grade ≥ 3 toxicity
 - During Cycle 1, a delay in dosing is not required for Grade 3 total bilirubin ≤ 3.5 mg/dL

NOTE: If bilirubin worsens after the first dose of nivolumab, a delay in dosing may be warranted per physician discretion.

- Any adverse event, laboratory abnormality, or intercurrent illness which, in the judgment of the investigator, warrants delaying the dose of study medication.

Immuno-oncology (I-O) agents are associated with AEs that can differ in severity and duration than AEs caused by other therapeutic classes. Nivolumab is considered an immuno-oncology agent in this protocol. Early recognition and management of AEs associated with immune-oncology agents may mitigate severe toxicity. Management Algorithms have been developed to assist investigators in assessing and managing the following groups of AEs:

- Gastrointestinal
- Renal
- Pulmonary
- Hepatic
- Endocrinopathy
- Skin
- Neurological

The above algorithms are found in the nivolumab Investigator Brochure and appendix 3 of this protocol.

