
Grades 3 or 4 Severe reaction, Grade 3: prolonged [i.e., not rapidly responsive to symptomatic medication and/or brief interruption of infusion]; recurrence of symptoms following initial improvement; hospitalization indicated for other clinical sequelae [e.g., renal impairment, pulmonary infiltrates]. Grade 4: Life-threatening; pressor or ventilatory support indicated
	
Immediately discontinue infusion of nivolumab. Begin an IV infusion of normal saline and treat the subject as follows: Recommend bronchodilators, epinephrine 0.2 to 1 mg of a 1:1000 solution for subcutaneous administration or 0.1 to 0.25 mg of a 1:10,000 solution injected slowly for IV administration, and/or diphenhydramine 50 mg IV with methylprednisolone 100 mg IV (or equivalent), as needed.
 
Subject should be monitored until the Investigator is comfortable that the symptoms will not recur. Nivolumab will be permanently discontinued. Investigators should follow their institutional guidelines for the treatment of anaphylaxis. Remain at bedside and monitor subject until recovery of the symptoms
 
In case of late-occurring hypersensitivity symptoms (e.g., appearance of a localized or generalized pruritus within 1 week after treatment), symptomatic treatment may be given (e.g., oral antihistamine or corticosteroids
	
No subsequent dosing

4.4.3 Treatment Discontinuation Criteria:

Tumor assessments for all subjects should continue every 8 weeks or 12 weeks once beyond 13 months of therapy, as per protocol, even if dosing is held or delayed.

Nivolumab treatment should be permanently discontinued for the following:

- Any Grade 2 drug-related uveitis, eye pain, or blurred vision that does not respond to topical therapy and does not improve to Grade 1 severity within the re-treatment period OR requires systemic treatment
- Any Grade 3 non-skin, drug-related adverse event lasting > 7 days, with the following exceptions: for laboratory abnormalities, drug-related uveitis,

pneumonitis, bronchospasm, hypersensitivity reactions, infusion reactions, and endocrinopathies:

- Grade 3 drug-related uveitis, pneumonitis, bronchospasm, hypersensitivity reaction, or infusion reaction **of any duration** requires discontinuation
- Grade 3 drug-related endocrinopathies adequately controlled with only physiologic hormone replacement do not require discontinuation
- Grade 3 drug-related laboratory abnormalities do not require treatment discontinuation except:

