 - Any Grade 3 drug-related thrombocytopenia > 7 days or associated with bleeding requires discontinuation
- Any drug-related liver function test (LFT) abnormality that meets the following criteria require discontinuation:
 - AST or ALT > 5-10 x ULN for > 2 weeks
 - AST or ALT > 10 xULN
 - Total bilirubin > 5 x ULN
 - Concurrent AST or ALT > 3 xULN and total bilirubin > 2 x ULN
- Any Grade 4 drug-related adverse event or laboratory abnormality, except for the following events which do not require discontinuation:
 - Grade 4 neutropenia ≤7 days
 - Grade 4 lymphopenia or leukopenia
 - Isolated Grade 4 amylase or lipase abnormalities that are not associated with symptoms or clinical manifestations of pancreatitis. The PI and DSMC should be consulted for Grade 4 amylase or lipase abnormalities.
 - Isolated Grade 4 electrolyte imbalances/abnormalities that are not associated with clinical sequelae and are corrected with supplementation/appropriate management within 72 hours of their onset
 - Grade 4 drug-related endocrinopathy adverse events, such as adrenal insufficiency, ACTH deficiency, hyper- or hypothyroidism, or glucose intolerance, which resolve or are adequately controlled with physiologic hormone replacement (corticosteroids, thyroid hormones) or glucose-controlling agents, respectively, may not require discontinuation.
- Any event that leads to interruption in dosing lasting > 6 weeks from the previous dose requires discontinuation, with the following exceptions:
 - Dosing interruptions to allow for prolonged steroid tapers to manage drug-related adverse events are allowed. Prior to re-initiating treatment in a subject with a dosing interruptions lasting > 6 weeks from the previous dose, the PI and DSMC must be consulted. Tumor assessments should continue as per protocol even if dosing is interrupted. Periodic study visits to assess safety and laboratory studies should also continue every 6 weeks or more frequently if clinically indicated during such dosing interruptions.

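### The Appendix 3 hepatic footnote permits delay where Section 4.4.3 requires permanent discontinuation, and no text says which governs

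*Combined protocol and SAP*

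**What the plan says.** Section 4.4.3 (Treatment Discontinuation Criteria) opens with "Nivolumab treatment should be permanently discontinued for the following". Its liver item reads "Any drug-related liver function test (LFT) abnormality that meets the following criteria require discontinuation" and lists four criteria:

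- AST or ALT above 5x to 10x ULN for more than 2 weeks
- AST or ALT above 10x ULN
- total bilirubin above 5x ULN
- "Concurrent AST or ALT > 3 xULN and total bilirubin > 2 x ULN", with no duration attached

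Appendix 3 is headed "Recommended management algorithms for suspected nivolumab related endocrinopathy, gastrointestinal toxicity, hepatotoxicity" and continues with the other organ systems. The footnote to its hepatic algorithm reads "I-O therapy may be delayed rather than discontinued if AST/ALT ≤ 8 x ULN or T.bili ≤ 5 x ULN".

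Three places bear on how a reader moves between these texts:

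- **Section 4.4 overview.** It says "Nivolumab may be delayed or discontinued following the instructions detailed in section 4.4.1" and then "In addition, nivolumab should be discontinued for toxicities as outlined in section 4.4.2". Section 4.4.2 deals with infusion reactions.
- **Section 4.4.1.** It says "Management Algorithms have been developed to assist investigators in assessing and managing the following groups of AEs" and gives Appendix 3 and the Investigator Brochure as their location. It states no order of precedence.
- **Section 4.4.4.** It names 4.4.3 correctly as the discontinuation criteria, but in the setting of treatment beyond progression.

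**The concern.** The footnote is worded as an exception to stopping, so a treating physician could take it as the specific rule that qualifies the general one in 4.4.3. The two texts lead to different outcomes for the same patient: re-dosing after recovery, or the permanent end of nivolumab.

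The combination at issue is one the protocol treats as a serious liver signal elsewhere. Section 7.2.12 uses the same two laboratory thresholds, with further conditions, to define potential drug-induced liver injury. The population has liver cancer, may be Child-Pugh B up to B8 (Section 3.1.1), and receives Y-90 before nivolumab, so decisions on liver tests will arise.

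The overview makes the conflict harder to resolve. A reader who follows it reaches the footnote through 4.4.1 and is given no pointer to the liver stopping criteria.

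**Working it through.** No sample-size or error-rate figure is involved. The check is to write both texts as rules and apply them to the same values. A is AST or ALT and B is total bilirubin, both in multiples of ULN.

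**Rules**

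- Section 4.4.3, stop: (5 < A ≤ 10 for more than 2 weeks), or A > 10, or B > 5, or (A > 3 and B > 2).
- Appendix 3 footnote, delay allowed, literal reading: A ≤ 8 or B ≤ 5.
- Appendix 3 footnote, delay allowed, narrower reading: A ≤ 8 and B ≤ 5.

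**Test values**

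| A | B | Duration | 4.4.3 | Footnote, *or* | Footnote, *and* | Result |
|---|---|---|---|---|---|---|
| 6 | 4 | any | stop (6 > 3, 4 > 2) | delay | delay (6 ≤ 8, 4 ≤ 5) | conflict on both readings |
| 8 | 5 | any | stop (8 > 3, 5 > 2) | delay | delay | conflict on both readings |
| 9 | 4 | any | stop (9 > 3, 4 > 2) | delay | not met | conflict on *or* only |
| 12 | 1 | any | stop (12 > 10) | delay | not met | conflict on *or* only |
| 1 | 6 | any | stop (6 > 5) | delay | not met | conflict on *or* only |
| 6 | 1 | 1 week | no criterion met | delay | delay | agree |
| 6 | 1 | 3 weeks | stop (over 2 weeks) | delay | delay | weak: can be read as delay, then stop |

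**Size of the conflict.** The finding uses the narrower reading. The concurrent criterion (A > 3, B > 2) then overlaps the footnote (A ≤ 8, B ≤ 5) for A above 3 up to 8 with B above 2 up to 5, at any duration.

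**Allowance for the missing flowchart.** The algorithm figure is not shown. The Amendment 3 entry in Appendix 5 describes its discontinuation step as AST/ALT > 5x or bilirubin > 3x ULN. If that is the step the footnote modifies (an assumption), the corner with A ≤ 5 and B ≤ 3 leaves the zone. The 6x/4x case remains, since 6 > 5 and 4 > 3.

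**Strength of the re-dosing safeguard.** Section 4.4.1 requires resolution to Grade 1 or less, or to baseline, before dosing resumes. The hepatic limits in Section 3.1.9 are AST and ALT ≤ 5x and bilirubin ≤ 3x ULN. A patient entering at 4x and 2.5x passes both limits (4 ≤ 5, 2.5 ≤ 3) yet already lies above both concurrent thresholds (4 > 3, 2.5 > 2). For such a patient, return to baseline does not bring the values below the level at which 4.4.3 calls for a stop when the abnormality is drug-related.

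**The case against.** The strongest reply is that this is a permission set against a requirement. Section 4.4.3 uses mandatory language. Appendix 3 is presented as recommended, its footnote says only that delay is possible, and 4.4.1 describes the algorithms as an aid. An investigator who follows 4.4.3 breaches nothing in Appendix 3. That is a fair reading and probably the intended one, but the reader has to infer it. The footnote is framed as an alternative to stopping, which invites the opposite inference.

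The missing flowchart is a real limit: it might carry its own restriction on concurrent elevation. The finding therefore rests on the footnote text alone.

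Reporting under Section 7.2.12 brings many such cases to the quality assurance monitor and the company within 24 hours, and then to the data and safety monitoring committee. It does not decide whether the patient is re-dosed, and it excludes cases with cholestasis or another apparent cause, including pre-existing liver disease.

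It can also be said that making 4.4.3 govern is hard on patients who enter with abnormal liver tests, because 4.4.3 has no baseline exception. That consequence already follows from 4.4.3 as written; the precedence rule does not create it.

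The wrong section number is an editorial slip and does not cause the conflict. Section 4.4.2 does contain a stopping rule for Grade 3 or 4 infusion reactions, so the pointer is incomplete, not empty.

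**Conclusion.** The concern holds. For drug-related AST/ALT above 3x up to 8x with bilirubin above 2x up to 5x ULN, Section 4.4.3 requires permanent discontinuation while the Appendix 3 footnote permits delay, and no visible sentence sets precedence. If the flowchart triggers are those in the Amendment 3 entry, the zone excludes AST/ALT ≤ 5x with bilirubin ≤ 3x. The case for isolated AST/ALT above 5x beyond 2 weeks is weaker and is not relied on.

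The weight is that of a minor safety-conduct correction that should be made. How often patients would reach the zone cannot be estimated from the documents. The MTD rules, response-rate analysis, sample size and error rates are unaffected.

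**What to change.** 1. In Section 4.4.1, after the reference to Appendix 3, and again beside the hepatic footnote, state that the liver criteria in Section 4.4.3 govern and that the delay option applies only when no Section 4.4.3 criterion is met.
2. In the Section 4.4 overview, change the second pointer from 4.4.2 to 4.4.3. Nothing is lost, because 4.4.3 also covers Grade 3 and 4 infusion reactions.

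No separate 8x threshold is needed. For example, AST 9x with bilirubin 1x for 1 week meets no 4.4.3 criterion (9 ≤ 10, duration not over 2 weeks, 1 ≤ 2), so delay under 4.4.1 stays available.

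The cost is amendment wording only: one rule in two places and one section number. The downside is a small addition to the algorithm text supplied by the company.
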